## **7 SUB-STUDY 4: A HEALTH ECONOMIC AND SOCIAL SCIENCE EVALUATION OF HEALTHCARE WORKER AND COMMUNITY KNOWLEDGE-ATTITUDES AND PRACTICES IN RELATION TO YAWS AND RELATED DISEASES, AND THEIR DIAGNOSIS.**

### **7.1 Objectives**

- 1) Collect data on community, patient and healthcare worker knowledge, attitudes and practices in relation to yaws and identify specific needs among the community including challenges in accessing prevention, care, and treatment services
- 2) Determine the acceptability and feasibility of TPHD-LAMP assay routine use
- 3) Determine cost-effectiveness of the TPHD-LAMP assay

### **7.2 Inclusion and exclusion criteria for objectives 1 and 2**

Inclusion criteria:

- Willingness to provide informed consent and assent to participation in the study
- Male or female and over the age of consent
- Male or female >12 and under the age of consent if accompanied by a parent or guardian
- Community members should be permanent residents in the selected communities

Exclusion

- Not able to give informed consent
- Under the age of consent with no parent/guardian available to accompany
- Not a permanent resident in the community

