## **5.6 Quality assurance for laboratory procedures at study sites**

The TPHD LAMP will be used at local hospital facilities close to the enrolled communities. Extensive training for this will take place prior to participant recruitment and we will conduct both internal and EQA activities throughout the study. Some aliquots of extracted DNA or additional lesion swabs will be exported to the European consortium laboratories and rechecked using both the TPHD-LAMP and gold standard (qPCR/PCR) for each pathogen. We will purposively select a higher proportion of samples for External Quality Assurance in the first six months of the laboratory testing to allow early detection of significant implementation problems. In case of significant differences between the reported results and the international reference laboratory results, an on-site evaluation will be initiated to identify the cause and solve the problem. All participating laboratories will work according to the GCLP guidelines, including internal quality assurance activities.

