### **7.3 Data collection**

Attitudes and practices in relation to yaws and identifying community needs: In each community, we will invite a sample of key groups including community health workers, opinion leaders and parents and guardians of children to participate in focus group discussions and semi-structured interviews about yaws and related skin diseases. As this is a qualitative evaluation, we have not performed a formal sample size calculation but will aim to achieve data saturation. For the community, members will be selected with an equal portion of males and females and a range of ages to ensure a representative sample. All focus group discussion and interviews will be conducted in English or French with local translators available if another language is preferred. All interviews and focus groups will be recorded, transcribed and translated if necessary. After being transcribed, recordings will be deleted. Common themes identified from the focus group discussions will be used to develop a questionnaire relating to their experiences and perceptions of: the cause of the disease and its transmission; its

diagnosis; healthcare seeking attitudes and factors (barriers/facilitators) influencing this. This questionnaire will be circulated to other communities and key stakeholders enabling us to obtain quantitative data to validate the hypotheses generated from the focus group discussions.

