Acceptability and feasibility: To assess the acceptability and feasibility of the TPHD-LAMP assay to healthcare workers and laboratory staff, we will conduct semi-structured interviews and/or use standardised questionnaires to gather their overall impressions of performing traditional molecular tests and the TPHD- LAMP assay. Again focus group discussion and interviews will be conducted in English or French with local translators available if another language is preferred. All interviews and focus groups will be recorded, transcribed and translated if necessary. After being transcribed, recordings will be deleted. For the feasibility aspect of the study, we will collect a range of information such as: determining the amount of training required to perform the test, for both field workers and laboratory staff, practicality of running the LAMP test in terms of laboratory space, reagent storage, electricity, sample transport and storage and other factors such as the time taken between sample collection and result and how easy it is to get the result back to the patient.

With patients and other key stakeholders, the test acceptability, will be explored via focus group discussions and in-depth interviews, with a focus on local knowledge and perceptions: of yaws and other skin conditions; diagnostics and available treatments, perceptions of healthcare workers' decisions in relation to yaws; and barriers to acceptability of the new test.

Cost-effectiveness: For the health-economic analysis we will use an “ingredients approach to costing”, gathering unit costs for each category of costing (training, personnel, capital costs, consumables, results storage and reporting, EQA, etc.). The costs of the LAMP assay will be compared with running the gold standard qPCR at national reference laboratories. The measure of effectiveness will be the number of additional yaws cases diagnosed and the number of additional yaws cases appropriately managed. If the macrolide resistance test can be successfully incorporated, then these costs will also be included, including the cost-savings of avoiding inappropriate antibiotic treatment.

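### Section 7.2 excludes every non-resident from sub-study 4 objectives 1 and 2, although its paired inclusion criterion limits residence to community members and the plan enrols healthcare workers, laboratory staff and stakeholders

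*Combined protocol and SAP*

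**What the plan says.** Section 7.2 is headed "Inclusion and exclusion criteria for objectives 1 and 2". It contains one inclusion list and one exclusion list, with no separate list for staff or stakeholders.

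- The inclusion criterion on residence is "Community members should be permanent residents in the selected communities".
- The exclusion on residence is "Not a permanent resident in the community".

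The populations for these objectives are set out elsewhere. Objective 1 in section 7.1 is to "Collect data on community, patient and healthcare worker knowledge, attitudes and practices in relation to yaws". For objective 2, section 7.3 introduces the interviews and questionnaires with "To assess the acceptability and feasibility of the TPHD-LAMP assay to healthcare workers and laboratory staff". Sections 1.3 and 3.1 name healthcare workers and key stakeholders as people to be enrolled in addition to community members or participants from the other sub-studies. Section 7.4 names healthcare workers, laboratory staff and patients as the groups for the thematic analysis of acceptance.

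On where the assay is run, section 5.6 says "The TPHD LAMP will be used at local hospital facilities close to the enrolled communities". Section 5.1 places the comparator qPCR/PCR at the national reference laboratory in each country.

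**The concern.** The two residence criteria do not match. The inclusion criterion applies to one group, and the exclusion applies to everyone on the list. An exclusion removes whoever meets it, so a non-resident laboratory technician who satisfies every inclusion criterion is still ineligible as written.

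This is an operative rule. Section 3.3 says that consent into each sub-study follows the relevant eligibility criteria and cites 7.2 by number. A site that applies the wording literally loses people who handle the assay. A site that ignores it enrols people against a stated criterion, and section 11 treats protocol violations as reportable to the ethics committee. Section 12 has separate national ethics reviews in three countries, so the sites could settle on different readings.

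The objectives at stake are primary ones in section 1.8: objective 2 (including acceptability and feasibility), objective 5 (including healthcare-worker knowledge, attitudes and practices) and the acceptability and feasibility part of objective 6.

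**Working it through.** No arithmetic applies. Section 7.3 says that no formal sample size calculation was made for the qualitative work, and the plan gives no figure on this point to reproduce. The check sets the eligibility text against the populations that the plan names.

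**Step 1: scope of the list.** The heading of 7.2 covers objectives 1 and 2 together, and no other eligibility list exists for them. Everyone enrolled under either objective therefore falls under it.

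**Step 2: the two residence criteria side by side.**

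| | Whom it covers | Where they must live |
|---|---|---|
| Inclusion | Community members | The selected communities |
| Exclusion | Not limited | The community (not defined) |

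**Step 3: result for each planned group under the literal wording.**

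| Group | Where planned | Result |
|---|---|---|
| Healthcare workers living permanently in a selected community | 7.1, 7.3 | Not barred |
| Healthcare workers living elsewhere | 1.3, 3.1, 7.1, 7.3, 7.4 | Barred |
| Laboratory staff living elsewhere | 7.3, 7.4 | Barred |
| Key stakeholders living elsewhere | 1.3, 3.1, 7.3 | Barred |
| Community health workers, opinion leaders, parents and patients living permanently in a selected community | 7.3 | Not barred |
| Respondents in other communities | 7.3 | Not settled by the exclusion; see step 5 |

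**Step 4: can non-resident staff be expected?** Section 5.6 puts the LAMP assay at hospitals near the enrolled communities, and section 5.5 puts it at district laboratory level. Nothing requires staff there to live in a selected community. Section 7.3 also wants staff to "gather their overall impressions of performing traditional molecular tests" as well as of the LAMP assay. With qPCR at the national reference laboratories (5.1), this suggests that their staff may be approached. That is an inference: the acceptability text in 7.3 refers only to healthcare workers and laboratory staff.

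**Step 5: the other communities.** Section 7.3 states "This questionnaire will be circulated to other communities and key stakeholders enabling us to obtain quantitative data". A respondent there may live permanently in their own community, so the exclusion does not clearly remove them. The criterion that could is the inclusion criterion, because it refers to the selected communities. That bites only if the other communities were not selected. Section 3.2 plans at least three districts per country, with the number of villages depending on prevalence, so other selected communities may be meant. The documents do not say.

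**The case against.** The strongest reply is that the intent is plain. The three exclusions follow the inclusion list: consent against consent, minors against an accompanying guardian, residence against residence. On that view, the residence exclusion is simply the negative of a criterion already limited to community members. A reading that removes healthcare workers also defeats the title of the sub-study. Much of the feasibility information in 7.3 is operational (training, laboratory space, storage, electricity, transport, turnaround time) and does not obviously depend on where an interviewee lives. The cost-effectiveness objective falls outside 7.2 altogether.

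Most of this stands. The intent can be inferred, the defect is one of drafting, and the consequence is modest. But the wording of the exclusion still contradicts its pair and the planned populations, and section 3.3 makes the list the rule for enrolment. An eligibility criterion should not have to be read against its own words.

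Three stronger readings are tempting, and the documents do not support them:

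- A reader might infer that hospital staff, reference-laboratory staff and stakeholders are barred as groups. Only those who are not permanent residents are barred, and reference-laboratory staff are not named as participants.
- A reader might infer that most staff, or a large share of sub-study 4 enrolments, would be affected. The documents give neither places of residence nor planned numbers.
- A reader might infer that the questionnaire cannot leave the communities that generated its themes. That needs the other communities to be unselected, which is not stated.

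**Conclusion.** The point holds as an internal contradiction in a stated eligibility rule. As written, 7.2 excludes healthcare workers, laboratory staff and key stakeholders who do not live permanently in a selected community, while other sections plan to enrol them. This takes the undefined community in the exclusion to mean a selected community, as in the inclusion criterion.

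The size cannot be stated. It could range from none of these participants, if all are residents, to all of them, if none are. Diagnostic accuracy, the sample sizes and every planned estimate are untouched.

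Whether the questionnaire's other communities also conflict with 7.2 is an open question for the sponsor, not a finding. The correction is worth making because it protects sources of evidence for primary objectives 2, 5 and 6 and costs almost nothing.

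**What to change.** In 7.2:

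1. Limit the residence exclusion to community members who are not permanent residents of a selected community, so that it mirrors the inclusion criterion.
2. Add a sentence stating that the residence criterion does not apply to healthcare workers, laboratory staff or key stakeholders.

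Separately, state in 7.3 whether the other communities that receive the questionnaire are among the selected communities. If they are, 7.2 needs no further change on that account. If they are not, the inclusion criterion and 7.3 must be reconciled.

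The cost is a small wording amendment, with no added participants, procedures or analyses.

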### **7.3 Data collection**

Attitudes and practices in relation to yaws and identifying community needs: In each community, we will invite a sample of key groups including community health workers, opinion leaders and parents and guardians of children to participate in focus group discussions and semi-structured interviews about yaws and related skin diseases. As this is a qualitative evaluation, we have not performed a formal sample size calculation but will aim to achieve data saturation. For the community, members will be selected with an equal portion of males and females and a range of ages to ensure a representative sample. All focus group discussion and interviews will be conducted in English or French with local translators available if another language is preferred. All interviews and focus groups will be recorded, transcribed and translated if necessary. After being transcribed, recordings will be deleted. Common themes identified from the focus group discussions will be used to develop a questionnaire relating to their experiences and perceptions of: the cause of the disease and its transmission; its

diagnosis; healthcare seeking attitudes and factors (barriers/facilitators) influencing this. This questionnaire will be circulated to other communities and key stakeholders enabling us to obtain quantitative data to validate the hypotheses generated from the focus group discussions.

Acceptability and feasibility: To assess the acceptability and feasibility of the TPHD-LAMP assay to healthcare workers and laboratory staff, we will conduct semi-structured interviews and/or use standardised questionnaires to gather their overall impressions of performing traditional molecular tests and the TPHD- LAMP assay. Again focus group discussion and interviews will be conducted in English or French with local translators available if another language is preferred. All interviews and focus groups will be recorded, transcribed and translated if necessary. After being transcribed, recordings will be deleted. For the feasibility aspect of the study, we will collect a range of information such as: determining the amount of training required to perform the test, for both field workers and laboratory staff, practicality of running the LAMP test in terms of laboratory space, reagent storage, electricity, sample transport and storage and other factors such as the time taken between sample collection and result and how easy it is to get the result back to the patient.

With patients and other key stakeholders, the test acceptability, will be explored via focus group discussions and in-depth interviews, with a focus on local knowledge and perceptions: of yaws and other skin conditions; diagnostics and available treatments, perceptions of healthcare workers' decisions in relation to yaws; and barriers to acceptability of the new test.

Cost-effectiveness: For the health-economic analysis we will use an “ingredients approach to costing”, gathering unit costs for each category of costing (training, personnel, capital costs, consumables, results storage and reporting, EQA, etc.). The costs of the LAMP assay will be compared with running the gold standard qPCR at national reference laboratories. The measure of effectiveness will be the number of additional yaws cases diagnosed and the number of additional yaws cases appropriately managed. If the macrolide resistance test can be successfully incorporated, then these costs will also be included, including the cost-savings of avoiding inappropriate antibiotic treatment.

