#### **1.7 Research question/Aim:**

LAMP4Yaws is a multidisciplinary study aiming to determine whether the *T. pallidum* and *H. ducreyi* Loop-mediated isothermal amplification (TPHD LAMP) test is suitable, feasible and cost-effective for use in national yaws eradication programmes and/or routine yaws surveillance. The main aim is supported by additional, linked social science and laboratory analysis that we hope will allow us to learn more about risk factors associated with disease, local transmission dynamics, other skin conditions and build in country capacity to run efficient yaws eradication campaigns.

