### **2.1.3 Diagnostics**

Accurately diagnosing yaws will be key to the success of the global eradication campaign.

Traditionally, serological tests have been the mainstay of yaws diagnosis, consisting of detection of treponemal and non-treponemal antibodies. Anti-treponemal antibodies are long-lived so are useful for indicating exposure but cannot distinguish between current and past infections, nor can they distinguish between infection with any of the *T. pallidum* subsp. *pallidum* (syphilis), *pertenue* (yaws), *endemicum* (bejel) or *T. carateum* (pinta). Non-treponemal tests are used to predict a current infection, but lack specificity. When used in conjunction non-treponemal and treponemal tests are a better indicator of a current treponemal infection, but also fail to distinguish between different species of Treponemes, and have been shown to miss early cases of yaws, which could be important for identifying resurgence of the disease after MDA.

Clinical diagnosis based on lesions alone is unreliable, often due to the presence of co-endemic ulcer-causing diseases. Recent studies using molecular tools have demonstrated only one third of yaws-like ulcers are positive for *T. pallidum*. Studies from Papua New Guinea and Solomon Islands have shown *H. ducreyi*, the causative agent of chancroid, to be responsible for a further third of these clinically-indistinguishable lesions. Often neither *T. pallidum* nor *H. ducreyi* are detected in these lesions and it is possible another infectious agent is responsible. Therefore, we will conduct further investigations to determine if other pathogens may be routinely detected that could influence the design of yaws eradication programs.

The urgent need for novel diagnostics is perhaps most essential in light of the emergence of azithromycin-resistant TPE. These strains have been shown to emerge independently, and have led to localized transmission. Highly sensitive and specific nucleic acid amplification tests (NAATs) which include tests for azithromycin resistance are available. However, these tests are often inaccessible and have limited use in the field setting. In light of this emerging macrolide resistance it is clear that more robust laboratory-based surveillance is required.

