### **2.1.4 Significance and Scientific Rationale**

Improved understanding of yaws transmission and novel yaws diagnostics are urgently needed to support the WHO eradication campaign. Current WHO strategy is based on clinical case searches combined with serological point of care (POC) assays. An improved understanding of yaws epidemiology, informed by diagnostics, would help refine and improve case search approaches and contact tracing as part of eradication efforts. Given the limitations of existing diagnostics, improved diagnostic tests are needed. These tests should be designed to fulfil the WHO REASSURED criteria, i.e. allow for real-time connectivity, easy to collect specimens, be affordable, sensitive, specific, user-

friendly, rapid, equipment-free and deliverable to end users . The TPHD LAMP test (Mast Diagnostica GmbH, Germany) is a POC test that is practical to use in resource-limited areas. LAMP does not require expensive equipment, such as thermocyclers required for traditional NAATs, and the reagents have been designed to be stored lyophilised for field conditions. The TPHD LAMP test can rapidly identify an infection with *T. pallidum* or *H. ducreyi* and has been shown to have high sensitivity and specificity in the laboratory . It can also be adapted to include azithromycin resistance detection . This test may, therefore, provide a suitable solution to the problems faced by current yaws diagnostics and if accurate and feasible to use in the field, has the potential to be used by yaws eradication programs, allowing for systematic real-time detection of *T. pallidum* and *H. ducreyi*, as well as azithromycin-resistant strains.

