## **5.7 Data Analysis**

For the evaluation of the TPHD-LAMP assay compared to qPCR for the diagnosis of yaws, we will calculate the sensitivity and specificity of the *T. pallidum* and *H. ducreyi* targets individually compared to the respective reference qPCR assays. We may perform additional sub-analyses to assess if the performance of the TPHD-LAMP assay is related to bacterial load as measured by qPCR. The positive predictive value and negative predictive value will also be determined against the qPCR results.

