## 7.4 Data Analysis

- 1) This will involve a mixed methods analysis. We will perform thematic analyses to identify common themes arising from focus group discussions and in-depth interviews. The quantitative questionnaires will be analysed using standard statistical analyses, including Chi

squared tests and logistic regression to analyse relationships between reported knowledge, attitudes and practices, and demographic variables such as gender, age and location.

- 2) For the feasibility and acceptability analysis we will also perform thematic analysis to generate themes of acceptance of the TPHD-LAMP assay amongst healthcare workers, laboratory staff and patients.
- 3) Cost-effectiveness: This analysis will involve using a decision tree model to weigh up the costs attributed to either test. The model will include the sensitivity and specificity of both tests, costs of person time required to perform the test and other variables that will affect if the TPHD-LAMP assay is suitable for routine diagnostics and surveillance.

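### The cost-effectiveness model compares LAMP only with reference-laboratory qPCR, so LAMP's value relative to current practice (clinical examination plus point-of-care serology) is not estimated

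*Combined protocol and SAP*

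**What the plan says.** Section 1.7 makes it part of the main aim to decide whether the LAMP "test is suitable, feasible and cost-effective for use in national yaws eradication programmes and/or routine yaws surveillance", and cost-effectiveness is repeated as primary objective 6 in 1.8. On present practice, 2.1.4 states: "Current WHO strategy is based on clinical case searches combined with serological point of care (POC) assays". Of conventional nucleic acid tests, 2.1.3 says that "these tests are often inaccessible and have limited use in the field setting".

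The economic plan is short. Section 7.3 names one cost comparator: "The costs of the LAMP assay will be compared with running the gold standard qPCR at national reference laboratories". The next sentence gives the effect measure: "The measure of effectiveness will be the number of additional yaws cases diagnosed and the number of additional yaws cases appropriately managed". Section 7.4(3) then describes the model: "This analysis will involve using a decision tree model to weigh up the costs attributed to either test". On inputs it adds: "The model will include the sensitivity and specificity of both tests". The same sentence goes on to staff time and other variables bearing on LAMP's suitability for routine use. Earlier in 7.3, turnaround and the return of results to patients are listed as feasibility data.

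LAMP accuracy comes from 5.7, which computes sensitivity and specificity for the *T. pallidum* and *H. ducreyi* "targets individually compared to the respective reference qPCR assays".

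**The concern.** The model has two branches, LAMP and qPCR. Their comparison says where a molecular test should be run. It does not say whether a programme that now relies on clinical examination and rapid serology should pay for LAMP. No section costs the current algorithm, gives it accuracy inputs or makes it a branch, so a stated primary objective would go unanswered for its main users.

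The effect measure adds two difficulties. First, if *additional* means additional to qPCR, the baseline is also the standard against which LAMP is scored, and the plan does not say what could produce a gain. Second, the plan does not say where LAMP would sit: after a dual-positive DPP, alongside serology for all lesions, or in place of serology. Against current practice, that choice and the case definition can decide whether the same data show a loss, no change or a gain.

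**Working it through.** **Inputs from the documents.** 6,000 people with yaws-like lesions and 600 dual DPP-positive (1.5, 4.3); 35% of seropositives qPCR-positive (5.3); 1 in 10 seronegative suspected cases swabbed (1.3, 4.5, 5.3); LAMP sensitivity and specificity to be confirmed as at least 85% (5.3).

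**Reproducing the plan's figure.** 600 × 0.35 = 210 qPCR-positive *T. pallidum* cases, as 5.3 states. It follows that 600 − 210 = 390 seropositive people are qPCR-negative, 6,000 − 600 = 5,400 lesion patients are seronegative, and about 540 of these are swabbed.

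**Assumed.** LAMP sensitivity (Se), LAMP specificity (Sp), and p, the qPCR-positive share of the 5,400. The documents do not give p; the range used is 0 to 5%. qPCR is treated as error-free.

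**LAMP versus qPCR, same patients.** Additional qPCR-confirmed cases = 210 × (Se − 1):

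| Se | Additional cases | Relative reach needed to break even (1/Se) |
|---|---|---|
| 85% | −31.5 | 1.18 |
| 90% | −21 | 1.11 |
| 95% | −10.5 | 1.05 |
| 100% | 0 | 1.00 |

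The figure cannot be positive on accuracy alone. A gain has to come from reach, completion or turnaround, or from qPCR error.

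**LAMP versus current practice, Se = 90%.**

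- *After a dual-positive DPP:* everyone tested is already a case under the algorithm, so no case can be added whatever p is. LAMP would be positive in 0.90 × 210 = 189 of the 210.
- *Added to serology for all lesions:* 0.90 × 5,400 × p = 0, 49, 97 and 243 at p = 0, 1%, 2% and 5%.
- *Replacing serology:* 0.90 × (210 + 5,400p) − 210 = −21, +28, +76 and +222 at the same values.

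**Effect of the case definition.** Section 4.3 defines active yaws as lesions confirmed serologically, which gives 600. Take LAMP replacing serology, p = 2%, Se 90%, Sp 95%, and count every test-positive person:

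- LAMP-positive and qPCR-positive: 0.90 × (210 + 108) = 286.2
- LAMP-positive and qPCR-negative: 0.05 × (390 + 5,292) = 284.1
- Total 570.3, against 600: about −30

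The same scenario gives +76 when only qPCR-confirmed cases count.

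**Precision available.** If 11 of 540 seronegative swabs are qPCR-positive, p is 2.04% (exact 95% CI 1.02% to 3.62%). Multiplied by 5,400 × 0.90, that is 99 cases (50 to 176). With LAMP replacing serology, 189 + 99 − 210 = +78 (+29 to +155). If 3 of 540 are positive, the contribution is 27 (6 to 78) and the net figure +6 (−15 to +58). These intervals treat the 1-in-10 as representative and ignore village clustering and uncertainty in Se. With 11 positives, LAMP sensitivity in seronegatives could hardly be checked: 10 of 11 is 91% (59% to 99.8%).

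**The case against.** The strongest defence is that the qPCR comparison is the intended one and a sound one. A district-level test is being weighed against a national reference-laboratory test, and unequal access is the reason for asking. The aim also covers surveillance, where detecting *H. ducreyi* and macrolide resistance matters, and antibody tests do neither. All of this stands, and the comparison should stay.

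A reader might infer that *additional* has no baseline at all. The documents do not support that: the sentence just before it in 7.3 names qPCR as the cost comparator, and 7.4(3) speaks of two tests, so additional to qPCR is the natural reading. A reader might also infer that LAMP can never show a gain over qPCR. That too goes too far. The equal-reach condition in the first table is ours, 7.4(3) admits other variables, and 7.3 collects turnaround and return of results. What is missing is a statement that these enter the effect measure. Nor do other variables in a two-test tree amount to a third strategy.

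Finally, the counts against current practice rest on an assumed p and assumed accuracy, and no costs are available. They show that the effect measure can change sign. They do not show that a cost-effectiveness conclusion would.

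**Conclusion.** The concern holds in this form: followed as written, 7.3 and 7.4(3) compare LAMP with qPCR and leave its cost-effectiveness relative to current practice unestimated. This gap does not depend on p. With qPCR as baseline, the accuracy component lies between −31.5 and 0 of 210 for sensitivity from 85% to 100%. Against current practice it is zero if LAMP follows a dual-positive DPP. It runs from −21 to +222 qPCR-confirmed cases if LAMP replaces serology at 90% sensitivity with p of 0 to 5%. It is about −30 at p = 2% and 95% specificity if all test-positives are set against the 600 of section 4.3. These ranges assume error-free qPCR and the plan's expected 600 and 35%.

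Sections 4.7 and 8.2 offer treatment or referral regardless of the screening result. A reader might infer that the difference in cases appropriately managed must therefore be zero. That would follow only if the term meant being offered treatment or referral, a definition the documents do not adopt; those sections describe what study participants receive, not what a programme model must assume. The supportable point is that the term is undefined for the model.

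The plan should be changed here, but the diagnostic accuracy study is unaffected.

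**What to change.** In 7.3 and 7.4(3):

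1. Add the current algorithm as a third strategy: clinical examination, SD Bioline, then DPP if positive, with SD Bioline-negatives coded as algorithm-negative. Give it its own unit costs and take its results from data already being collected. Weight the 1-in-10 seronegative swabs by 10 and carry their uncertainty through. Keep LAMP versus qPCR.
2. For each comparison, state the baseline for *additional*, the case definition (qPCR-positive or serologically confirmed) and where LAMP sits in the pathway. Report test-positive, qPCR-negative people on a separate line, including the roughly 390 expected among seropositives.
3. State that reach, test completion and turnaround enter the effect measure, and vary them and qPCR accuracy in sensitivity analysis.
4. Define appropriate management for the model and say what it is compared with, in view of 4.7 and 8.2. This is a modelling definition only; no treatment rule is proposed.

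The cost is one more model branch, unit costs for two rapid tests already in use, and explicit reach and completion inputs. No new samples are needed. The limits are that the seronegative contribution will be imprecise, with about 540 swabs, and that it assumes LAMP sensitivity carries over from seropositive to seronegative lesions. The weighting also presumes that the swabbed tenth represents all seronegatives; how that tenth is drawn is a separate sampling question.
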